18.3. Appendix C: International Prognostic Scoring System Score

International Prognostic Scoring System for MDS					
Prognostic Variable	Score Value				
	0	0.5	1.0	1.5	2.0
Bone Marrow Blasts (%)	< 5	5-10	-	11-20	21-30
Karyotype ^a	Good	Intermediate	Poor		
Cytopenias ^b	0 or 1	2 or 3			

^a Good: normal, -Y, del(5q), del(20q); Poor: complex (≥ 3 abnormalities) or chromosome 7 anomalies; Intermediate: other abnormalities.

^b Defined as: Hemoglobin < 100 g/L, absolute neutrophil count $< 1.5 \times 10^9/L$, and platelet count $< 100 \times 10^9/L$.

Note: Scores for risk groups are as follows: Low = 0; INT-1 = 0.5-1.0; INT-2 = 1.5-2.0; and High: ≥ 2.5

Source: Greenberg, P, Cox C, LeBeau MM, Fenaux P, Morel P, Sanz G, et al. International scoring system for evaluating prognosis in myelodysplastic syndromes. Blood 1997;89:2079-88.

18.4. Appendix D: ECOG Performance Status

ECOG Performance Status	
Grade	ECOG
0	Fully active, able to carry on all pre-disease performance without restriction.
1	Restricted in physically strenuous activity but ambulatory and able to carry out work of a light or sedentary nature, eg, light house work, office work.
2	Ambulatory and capable of all selfcare but unable to carry out any work activities. Up and about more than 50% of waking hours.
3	Capable of only limited selfcare, confined to bed or chair more than 50% of waking hours.
4	Completely disabled. Cannot carry on any selfcare. Totally confined to bed or chair.
5	Dead.

Source: Oken MM, Creech RH, Tormey DC, Horton J, Davis TE, McFadden ET, et al. Toxicity and response criteria of the Eastern Cooperative Oncology Group. Am. J. Clin. Oncol. 1982;5(6):649-55.

18.5. Appendix E: Hematologic Response According to the IWG Criteria for MDS

Modified Hematologic Response According to IWG Criteria for MDS	
Category	Response criteria (responses must last at least 4 weeks)
Complete Remission (CR)	Bone marrow: $\leq 5\%$ myeloblasts with normal maturation of all cell lines ^a Persistent dysplasia will be noted ^{a,b} Peripheral blood ^c Hgb ≥ 11 g/dL Platelets $\geq 100 \times 10^9/L$ Neutrophils $\geq 1.0 \times 10^9/L^b$ Blasts 0%
Partial Remission (PR)	All CR criteria if abnormal before treatment except: Bone marrow blasts decreased by $\geq 50\%$ over pretreatment but still $> 5\%$ Cellularity and morphology not relevant
Marrow CR ^b	Bone marrow: $\leq 5\%$ myeloblasts and decrease by $\geq 50\%$ over pretreatment ^b Peripheral blood: if HI responses, they will be noted in addition to marrow CR ^b
Stable Disease (SD)	Failure to achieve at least PR, but no evidence of progression for > 8 wks
Failure	Death during treatment or disease progression characterized by worsening of cytopenias, increase in percentage of bone marrow blasts, or progression to a more advanced MDS FAB subtype than pretreatment
Relapse After CR or PR	At least 1 of the following: Return to pretreatment bone marrow blast percentage Decrement of $\geq 50\%$ from maximum remission/response levels in granulocytes or platelets Reduction in Hgb concentration by ≥ 1.5 g/dL or transfusion dependence
Cytogenetic Response	Complete - Disappearance of the chromosomal abnormality without appearance of new ones Partial - At least 50% reduction of the chromosomal abnormality
Disease Progression	For subjects with: Less than 5% blasts: $\geq 50\%$ increase in blasts to $> 5\%$ blasts 5%-10% blasts: $\geq 50\%$ increase to $> 10\%$ blasts 10%-20% blasts: $\geq 50\%$ increase to $> 20\%$ blasts 20%-30% blasts: $\geq 50\%$ increase to $> 30\%$ blasts Any of the following: At least 50% decrement from maximum remission/response in granulocytes or platelets Reduction in Hgb by ≥ 2 g/dL Transfusion dependence

KEY: CR = complete remission; DFS = disease-free survival; FAB = French-American-British; Hgb = hemoglobin; HI = hematologic improvement; IWG = International Working Group; MDS = myelodysplastic syndromes; PFS = progression free survival; PR = partial remission

^a Dysplastic changes should consider the normal range of dysplastic changes (modification).

^b Modification to IWG response criteria.

^d In some circumstances, protocol therapy may require the initiation of further treatment (eg, consolidation, maintenance) before the 4-week period. Such subjects can be included in the response category into which they fit at the time the therapy is started. Transient cytopenias during repeated chemotherapy courses should not be considered as interrupting durability of response, as long as they recover to the improved counts of the previous course.

Notes: Subjects with CMML will be assessed for response using the IWG criteria for MDS. Deletions to IWG response criteria are not shown. To convert hemoglobin from grams per deciliter to grams per liter, multiply grams per deciliter by 10.

Source: Cheson BD, Greenberg PL, Bennett JM, Lowenberg B, Wijermans PW, Nimer SD et al. Clinical application and proposal for modification of the International Working Group (IWG) response criteria in myelodysplasia. Blood 2006; 108 (2): 419-25.

Modified Hematologic Improvement According to IWG Criteria	
Hematologic improvement^a	Response criteria (responses must last at least 8 week)^b
Erythroid Response (HI-E) (pretreatment, <11 g/dL)	Hemoglobin increase by ≥ 1.5 g/dL Relevant reduction of units of RBC transfusions by an absolute number of at least 4 RBC transfusions/8 weeks compared with the pretreatment transfusion number in the previous 8 weeks. Only RBC transfusions given for a hemoglobin of ≤ 9.0 g/dL pretreatment will count in the RBC transfusion response evaluation ^b
Platelet Response (HI-P) (pretreatment, <100 X 10 ⁹ /L)	Absolute increase of ≥ 30 X 10 ⁹ /L for subjects starting with > 20 X 10 ⁹ /L platelets Increase from < 20 X 10 ⁹ /L to > 20 X 10 ⁹ /L and by at least 100% ^b
Neutrophil Response (HI-N) (pretreatment, <1.0 X 10 ⁹ /L)	At least 100% increase and an absolute increase > 0.5 X 10 ⁹ /L ^b
Progression or Relapse After HI ^c	At least 1 of the following: At least 50% decrement from maximum response levels in granulocytes or platelets Reduction in hemoglobin by ≥ 1.5 g/dL Transfusion dependence

KEY: HI = hematologic improvement; HI-E = hematologic improvement erythroid response; HI-N = hematologic improvement neutrophil response; HI-P = hematologic improvement platelet response; IWG = International Working Group; MDS = myelodysplastic syndromes; RBC = red blood cell

a Pretreatment counts averages of at least 2 measurements (not influenced by transfusions) ≥ 1 week apart (modification).

b Modification to IWG response criteria.

c In the absence of another explanation, such as acute infection, repeated courses of chemotherapy (modification), gastrointestinal bleeding, hemolysis, and so forth. It is recommended that the 2 kinds of erythroid and platelet responses be reported overall as well as by the individual response pattern.

Note: Deletions to the IWG response criteria are not shown. To convert hemoglobin levels from grams per deciliter to grams per liter, multiply grams per deciliter by 10.

Source: Cheson BD, Greenberg PL, Bennett JM, Lowenberg B, Wijermans PW, Nimer SD et al. Clinical application and proposal for modification of the International Working Group (IWG) response criteria in myelodysplasia. Blood 2006; 108 (2): 419-25.

18.6. Appendix F: Derivation Rules for Hematologic Response and Hematologic Improvement According to the IWG Criteria for MDS

Following rules will be used to derive the hematologic response, cytogenetic response, and hematologic improvement using central lab data, including [redacted] central lab data for bone marrow. Lab data collected after the date of the end of treatment visit, or last dose date + 28 days, whichever occurs later, will not be used.

In the following derivations, if Hgb or platelet counts are used for evaluation, the Hgb values are only valid to use if there is no RBC/Whole blood transfusion within 7 days prior to the sample collection, the platelet count values are only valid to use if there is no platelet transfusion within 7 days prior to the sample collection.

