
Neutropenia Grade 4 (related or unrelated to IP)
	
Pre-existing Neutropenia Grade 4
 
 • Subjects with G4 ANC at D1 of a cycle are going to be dosed for a maximum of 14 days on the respective dose level 300 mg or 200 mg or a maximum of 7 days when already on a 14-day dosing schedule. 
If subjects are stable or improving for several cycles, a discussion with the Medical Monitor is necessary to determine the dose schedule.
 
 • If dose was held, the start of next cycle is based on ANC recovery, see flow chart in Section 8.2.5 Re-Treatment Criteria • If the subject continues to experience neutropenia Grade 4 during 2 consecutive cycles, the treatment schedule may be reduced one step. Secondary prophylaxis with G-CSF is strongly recommended. 
Subjects experiencing worsening of Neutropenia to Grade 4 under IP treatment
 
 • Subjects that experience a drop in the ANC during a cycle (e.g., from G3 to G4 or for > 50% drop for subject with G4 at Day 15 or Day 8 [Day 8 during the 1st two cycles]) will hold the dose for the remaining cycle. 
If subject is stable or improving for several cycles, a discussion with the Medical Monitor is necessary to determine the dose schedule.
 
 • If dose was held, the start of next cycle is based on ANC recovery, see flow chart in Section 8.2.5 Re-Treatment Criteria.
	
 • If the subject continues to experience neutropenia Grade 4 during 2 consecutive cycles, the treatment may be reduced one step. Secondary prophylaxis with G-CSF is strongly recommended.

Table 2: Guidelines for Dose Modifications

NCI CTCAE Toxicity Grade	Action
Diarrhea (≥ Grade 3)	
 • Interrupt IP and provide adequate/maximum medical intervention • Resume IP at same dose when toxicity resolves to ≤ Grade 1 • If event reoccurs upon re-challenge or during next treatment cycle, reduce IP dose to 200 mg. • If event reoccurs at same intensity once IP dose is reduced to 200 mg, follow the steps above and modify the treatment schedule at a dose of 200 mg once a day.

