azacitidine may be appropriate. Pre- and post-treatment with an antidiarrheal must be recorded in the CRF as concomitant medication.

Myeloid growth factors (G-CSF and granulocyte macrophage colony-stimulating factor [GM-CSF]) may be given per investigator's discretion for the treatment of neutropenic fever/infections as well as for secondary prophylaxis (ie, prophylactic use of myeloid growth factors if the subject had a previous event of neutropenic fever/infection or neutropenia Grade 4 during the treatment phase of the study) and the safety of the patient is considered jeopardized by subsequent episodes of neutropenic fever/infections or Grade 4 neutropenia.

For subjects who develop an ANC $< 0.5 \times 10^9/L$, administration of prophylactic fluoroquinolone antibiotics (eg, ciprofloxacin or levofloxacin or other recognized prophylactic antibiotics) is strongly recommended and should be documented as a concomitant medication on the appropriate CRF. If neutropenic fever/infection occurs, treatment should consist of a broad spectrum antibiotic, and if the investigator deems the use of a myeloid growth factor to be medically important, myeloid growth factors may also be administered. In case of use of secondary prophylaxis with myeloid growth factors, the dose modification guidelines detailed in [Section 8.2.4](#) remain applicable. Discontinuation of secondary prophylaxis with myeloid growth factors should be considered by the investigator as clinically appropriate.

Concurrent corticosteroids for medical conditions other than MDS is allowed provided subject is on a stable or decreasing dose for ≥ 1 week prior to randomization.

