10.2.15. Hematologic response

Hematologic response (Complete Remission [CR], Partial Remission [PR], Marrow CR [mCR], Stable Disease [SD], Disease Progression [PD], Failure, Relapse after CR or PR, and Cytogenetic Response) is defined according to IWG 2006 criteria ([Appendix E](#)). Subjects will be classified according to their best response achieved during treatment for the response categories of CR, PR, mCR, SD, PD, and failure. Only subjects who achieve CR or PR will be included in the Relapse after CR or PR category. Subjects will be evaluated for cytogenetic response regardless of their response status in other categories. For cytogenetic response, subjects will be classified as having a complete or partial response based on the best response achieved during treatment. Hematologic response will be presented descriptively, by treatment group, using counts and percent. All above responses collected in the IWG MDS Response Criteria CRF will be summarized. In addition, hematologic response CR, PR, SD, mCR, relapse after CR or PR, cytogenetic response, and hematologic improvement will be derived using central labs per IWG criteria and will be summarized separately. The detailed derivation is provided in [Appendix F](#).

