18.6.3. Hematologic Improvement

Following rules will be used to derive the hematologic improvement using the central lab data.

- Platelet Response (HI-P):
 - Absolute increase of $\geq 30 \times 10^9/L$ for subjects starting with $> 20 \times 10^9/L$ platelets, or
 - Increase from $\leq 20 \times 10^9/L$ to $> 20 \times 10^9/L$ and by at least 100%.Platelet values within 7 days following a platelet transfusion will not be used.
- Erythroid Response (HI-E):
 - Hgb increase by ≥ 1.5 g/dL, or

- Relevant reduction of units of RBC transfusions by an absolute number of at least 4 RBC transfusions/8 weeks compared with the pretreatment transfusion number in the previous 8 weeks. Only RBC transfusions given for a Hgb of ≤ 10.0 g/dL on treatment will count in the RBC transfusion response evaluation.

Hgb values within 7 days following a RBC/Whole blood transfusion will not be used.

- Neutrophil Response (HI-N) (only derived for subjects with baseline ANC $< 1.0 \times 10^9/L$):
 - At least 100% increase and an absolute increase $> 0.5 \times 10^9/L$.

For HI-E, the relevant reduction of units of RBC transfusions is confirmed by checking whether a subject is a RBC transfusion reduction responder as defined in Section 10.2.11, ie., if the subject has at least 4 units reduction in transfusion units over a consecutive 56 days period compared to the baseline transfusion units in 56 days.

For HI-P, HI-E and HI-N, the above criteria must be met for at least 8 weeks for a subject to be counted as a responder. If a subject doesn't have the subsequent data which meet the response criteria, the subject will not be considered as a responder.

18.7. Appendix G: Revised International Prognostic Scoring System (IPSS-R) for Myelodysplastic Syndromes

The IPSS-R score will be derived per [Greenberg, 2012](#).

Table 2. IPSS-R Prognostic Score Values

Prognostic Variable	0	0.5	1.0	1.5	2.0	3	4
Cytogenetics	Very Good		Good		Intermediate	Poor	Very Poor
Bone Marrow Blast %	≤ 2		>2-<5%		5-10%	>10%	
Hemoglobin (g/dL)	≥10		8-<10	<8			
Platelets (x10 ⁹ /L)	≥100	50-<100	<50				
Absolute Neutrophil Count (x10 ⁹ /L)	≥0.8	<0.8					

Source: Greenberg PL, Tuechler H, Schanz J, Sanz G, Garcia-Manero G, Solé F, et al. Revised International Prognostic Scoring System for Myelodysplastic Syndromes. Blood 2012; 120: 2454-2465.

Table 3. IPSS-R Prognostic Risk Categories/Scores

RISK CATEGORY	RISK SCORE
Very Low	≤ 1.5
Low	> 1.5 – 3
Intermediate	> 3 – 4.5
High	> 4.5 – 6
Very High	> 6

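### The derived hematologic responses screen out transfusion-influenced hemoglobin and platelet values but have no matching rule for neutrophil counts taken under G-CSF or GM-CSF, so sustained growth-factor support can count as HI-N

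*SAP*

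**What the plan says.** The opening of SAP 18.6 (Appendix F) sets validity conditions for the derived responses. For hemoglobin, "the Hgb values are only valid to use if there is no RBC/Whole blood transfusion within 7 days prior to the sample collection". For platelets, "the platelet count values are only valid to use if there is no platelet transfusion within 7 days prior to the sample collection". No condition is attached to neutrophils.

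The absolute neutrophil count (ANC) enters the derivation in these places:

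- HI-N in SAP 18.6.3: "Neutrophil Response (HI-N) (only derived for subjects with baseline ANC" is below 1.0 x 10^9/L. The threshold is "At least 100% increase and an absolute increase" above 0.5 x 10^9/L, and "the above criteria must be met for at least 8 weeks for a subject to be counted as a responder".
- CR item 1(e) in SAP 18.6.1, carried into PR: neutrophils at least 1.0 x 10^9/L.
- The neutrophil limbs of derived progression and relapse, also in SAP 18.6.1.

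SAP 10.2.15 puts these results in the report: "cytogenetic response, and hematologic improvement will be derived using central labs per IWG criteria and will be summarized separately".

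Protocol 9.1 says that G-CSF and GM-CSF "may be given per investigator's discretion for the treatment of neutropenic fever/infections as well as for secondary prophylaxis". Protocol Table 2 states "Secondary prophylaxis with G-CSF is strongly recommended" for febrile neutropenia, and again for Grade 4 neutropenia that continues through two consecutive cycles.

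**The concern.** The two transfusion rules rest on a sound principle: a count raised by supportive care is not evidence of marrow response. The SAP applies that principle to two of three lineages. The protocol's amendment history, in its rationale for allowing secondary prophylaxis, itself says that these factors can raise neutrophil counts in MDS.

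What is at stake is the reading of a between-arm table. Protocol 1.4.1 names neutropenia and febrile neutropenia among the most frequent hematologic adverse events on oral azacitidine. If that leads to more sustained growth-factor use in that arm, part of any HI-N advantage would reflect management of toxicity. Nothing in the derived output would show it.

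**Working it through.** No design figure depends on this rule, so there is no stated number to reproduce. The check compares the rules and then works through what they allow.

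**1. Rules side by side**

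| Lineage | Supportive care | Validity rule (SAP 18.6) | Baseline rule (SAP 8.2) |
|---|---|---|---|
| Hemoglobin | RBC or whole blood transfusion | Void within 7 days after | Stepwise, to remove transfusion influence |
| Platelets | Platelet transfusion | Void within 7 days after | Same approach |
| ANC | G-CSF/GM-CSF | None | Last non-missing central value |

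Nothing elsewhere closes the gap. Protocol Appendix D and SAP Appendix E mention only transfusion influence on pretreatment counts. SAP section 16 and the planned sensitivity analyses do not mention growth factors. Protocol exclusion criterion 9 lists agents for red cells and platelets but not G-CSF, so baseline ANC is also unscreened.

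**2. What HI-N requires.** For baseline ANC b (x 10^9/L), the count must be at least 2b and above b + 0.5.

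- b = 0.3: at least 0.6 and above 0.8, so above 0.8.
- b = 0.5: at least 1.0 and above 1.0, so above 1.0.
- b = 0.9: at least 1.8 and above 1.4, so at least 1.8.

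**3. Duration.** Hematology is sampled every two weeks in Cycles 3 to 12 (Protocol 6.6.5). An 8-week run therefore spans about 56/14 + 1 = 5 scheduled samples. A short course for one febrile episode is unlikely to cover that; sustained secondary prophylaxis could.

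**4. CR and PR.** All five criteria must hold together for at least 4 weeks. Besides neutrophils, they are the marrow blast criterion, blood blasts 0%, hemoglobin at least 11 g/dL and platelets at least 100 x 10^9/L. The last two are transfusion-screened, and baseline marrow blasts must exceed 5%. Growth factor can supply one criterion of five.

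**5. Illustration of size.** Let r be the true HI-N rate (equal in both arms), g the share on sustained growth factor, and q the chance that a supported ANC meets HI-N for 8 weeks. All three are assumptions.

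Observed rate = r + (1 - r) x q x g, so the spurious difference = (1 - r) x q x (gA - gP), where A is azacitidine and P is placebo.

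With r = 0.05, in percentage points:

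| gA v gP | q = 0.25 | q = 0.50 | q = 0.75 |
|---|---|---|---|
| 10% v 10% | 0 | 0 | 0 |
| 20% v 10% | 2.38 | 4.75 | 7.13 |
| 30% v 10% | 4.75 | 9.50 | 14.25 |
| 40% v 5% | 8.31 | 16.63 | 24.94 |

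For example, 0.95 x 0.75 x (0.40 - 0.05) = 0.2494.

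A second set of assumptions is r = 0.10, use of 20-40% v 5-10%, and q of 0.30-0.60. It gives 0.90 x 0.30 x 0.10 = 2.7 points up to 0.90 x 0.60 x 0.35 = 18.9 points.

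**The case against.** The strongest case is that little rides on this. HI-N is not a listed endpoint of its own; only HI-P and HI-E are. Hematologic response is presented descriptively and carries no alpha. The IWG criteria as transcribed in both documents contain no growth-factor exclusion. All of that stands, and it limits the importance of the point.

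Four stronger readings are tempting, and the documents do not support them.

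- **G-CSF can create CR or PR.** It cannot. Four other criteria and the baseline blast condition must also be met.
- **Stopping G-CSF will be reported as progression.** The derivation does have a neutrophil limb: a fall of at least 50% to below 1.0, kept for 4 weeks. But progression is not among the central-laboratory results that SAP 10.2.15 summarizes. Subjects are classified by best response, and a subject already 8 weeks without progression has reached stable disease. Derived relapse arises only after CR or PR.
- **G-CSF use is higher on azacitidine.** This is an inference from the adverse-event profile. The Grade 4 recommendation applies whether or not the neutropenia is related to study drug, and it covers pre-existing Grade 4. Placebo subjects with low baseline ANC, the same group in which HI-N is derived, can therefore also qualify.
- **The baseline gap favors azacitidine.** A baseline raised by G-CSF makes HI-N harder or removes the subject from the HI-N set. It arises before randomization, so it has no treatment-driven direction.

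The illustration also takes q as equal between arms. Myelosuppression on azacitidine could lower q there and shrink the difference.

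**Conclusion.** The asymmetry is real, and nothing in either document offsets it. Followed as written, SAP 18.6 lets sustained G-CSF or GM-CSF support count as a derived HI-N response, and so as a hematologic improvement. It also lets such support complete a CR or PR that fails only on neutrophils.

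The descriptive HI-N comparison is biased if sustained use differs by arm. That is plausible but not reported. Its size cannot be obtained from the documents; the range of 0 to about 25 points rests wholly on assumed r, g and q and is not an estimate. RBC transfusion independence, OS, HI-P and HI-E are unaffected. This is worth correcting because the remedy is cheap, not because it threatens the confirmatory results.

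**What to change.** Add a rule to SAP 18.6 beside the two transfusion conditions:

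- An ANC taken on G-CSF or GM-CSF, or within a pre-specified and justified window afterwards, cannot count as meeting the HI-N criterion or CR/PR item 1(e).
- Values that fail the criterion are kept, whether or not growth factor was in use.
- A supported value is not replaced by the latest available result and is not itself carried forward.

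Simply voiding every supported ANC, as is done for transfusions, would be wrong. It would delete low values that disprove a response, and CR persistence asks only that no result within 4 weeks fails. It would also trigger the SAP 18.6.1 rule that fills a missing neutrophil value with the latest available one.

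At minimum, run HI-N and CR/PR this way as a sensitivity analysis. In either case, flag baseline ANC values taken on growth factor, and report G-CSF/GM-CSF use by arm from the concomitant-medication CRF.

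The cost is a short SAP rule and a merge of laboratory data with concomitant-medication dates already collected (SAP 5.1.1). The HI-N rate may fall. The documents give no window, so the sponsor must choose and defend one. Because the primary clinical study report is already final, any reanalysis should be labelled post hoc.
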